Two 1995 reports of sizeable samples found that CPAP is highly effective in controlling childhood SDB, and is well tolerated in more than 80% of patients. A smaller, randomized trial to compare CPAP with bilevel positive airway pressure (BPAP) found that one third of 29 participants aged 2 – 16 years dropped out by 6 months; CPAP and BPAP showed no difference in adherence or effectiveness; and mean nightly use recorded electronically was adequate on average ( $5.3 \pm 2.5$  hours per night) in subjects who finished the protocol. Parental reports of adherence exceeded electronically recorded adherence, just as subjective CPAP use among adults exceeds electronically monitored use. In a retrospective study of 46 children aged 7 – 19 years, all treated with PAP after AT, the intervention again controlled SDB well (in all subjects); 70% of subjects used PAP for more than 4 hours on 5 or more nights per week; parents overall estimated adherence well, though they overestimated machine use for those children documented to use it 4 hours or less per night; and adherence did not vary significantly by age, gender, BMI, or race. In another retrospective study, 65 of 79 children aged 6 months to 18 years successfully used PAP, with a mean daily use of 4.7 hours. The commitment and investment of the parents is particularly important. Initial trials of low pressure settings or behavioral intervention may be necessary in some cases. Behavioral therapy can include positive reinforcement, differential positive reinforcement, counterconditioning, and graduated exposure. These improved adherence in 75% of 20 non-compliant children in one study; parents usually considered the treatment successful and most reported improvements in children's mood, alertness, and learning.

These trials of PAP in children also show that the therapy is safe. Mid-face hypoplasia, a reported but

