Note that Addendum #1 provides for enrollment of subjects after adenotonsillectomy at or prior to study visit 2. This allows increased opportunity for interested families who are not able to schedule the pre-operative visit or who are referred to the study after their surgery to participate in this research. More information on this additional study arm is provided in the addendum and the MOP.

**C3. Procedures.** Each participant will undergo a baseline, pre-randomization evaluation of sleep and neurobehavioral variables at 4 months after AT, as several months are required to ensure complete healing. Most of the neurobehavioral benefit achieved after AT for SDB accrues in the first 3 months (unpublished data from the investigators). After baseline assessments, all subjects will be randomized to CPAP or non-CPAP (standard care) groups. Group assignments will be made using a randomization algorithm, possibly with automatic adjustment that prospectively ensures balance between groups for SDB status, residual post-operative SDB symptoms, gender, age and/or BMI. Non-CPAP families will be contacted by the program manager for 6 months at intervals designed to replicate the frequency and nature of investigator contacts in the CPAP group. Discussion will focus on recuperation after AT, general health, and any suggestion of serious adverse effects that would warrant discontinuation of study participation and referral for clinical evaluation. These end-points would include recommendations by a child's pediatrician or otolaryngologist to pursue this option; development of a new, serious cardiopulmonary condition that makes prompt assessment and treatment for any residual SDB imperative; or emergence of serious academic or developmental concerns in the setting of obvious, persistent symptoms of SDB. Each questionable case will be brought by the program manager to the PI (section 6.5) for a decision and possible notification of the DSMB per the Data and Safety Management Plan guidelines.

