- d) Failure to reinitiate CPAP therapy after a period off-treatment due to an upper respiratory illness or other interfering event.

The number and frequency of visits will depend on: (1) the child's current threshold; and (2) how the child and family advance through each step of the desensitization protocol. The decision to hold on a particular step of the desensitization program will be based on whether the homework was completed and/or whether the child's current level of anxiety or opposition is elevated. A recommendation to discontinue CPAP treatment may be made if the child or family has not progressed to another step in 2-4 weeks (depending on the number of visits during that time). Discontinuation of PAP treatment may occur after case consultation with other members of the study team to insure that all strategies have been considered. Additional effort to improve adherence is not desirable because this would not resemble practice available at most other clinical centers. In addition, varying levels of adherence will be necessary to test hypothesis 2b.

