The proposed protocol adheres to the ethical principles outlined by the National Commission for the Protection of Human Subjects of Biomedical and Behavioral Research. Respect for persons is maintained, as the adult parent or guardian with full capacity will provide written informed consent, a child over age 8 or able to understand the study will provide written assent, and a younger child will give verbal assent. The principle of beneficence is respected as for each participant the potential for personal benefit from this study will outweigh the small risks involved. This study will not subject any child to tests or treatments that stand no chance to benefit him or her personally. This follows from decisions made about the randomized control arm (see Introduction), which will involve only standard care and periodic contacts from investigators. No child will be deprived of needed medical care. Agreement to participate in this research will not prevent any family from withdrawing at any time. Although control subjects will receive no intervention beyond frequent contacts with investigators or the program manager, the investigators anticipate based on their previous research that few will leave the protocol to seek clinical care. Those contacts also will be used to ensure that any highly unlikely but conceivable situations in which absence of CPAP could pose an urgent medical threat will be detected early so that the subject can be removed from the study. Lastly, the principle of justice is respected because the population to be studied will be exactly that which stands to gain most from the results of the study.

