Some children in this protocol will use PAP without having enough underlying, residual SDB to benefit from the intervention. During the treatment trial, neither investigators nor families will know who these children are. Although symptoms may be readily apparent, sleep study results will not be available until after study participation is complete, for several reasons. One is that sleep studies are to be scored in batches -- with several subjects’ pre-PAP and post-PAP studies all in the same de-identified batch -- to avoid any influence of scoring drift over time. A second reason is that at present, knowledge about how post-AT care should be guided by sleep study results remains quite limited. The research now proposed, in fact, aims in large part to address this void.

Fortunately, subjects without residual SDB after AT, as compared to subjects with SDB, have no known additional risks to use of PAP. When the PAP titration studies are performed, children without SDB will have normal breathing, technologists will have no reason to test more than the lowest CPAP settings, and the reviewing physician (co-investigator [name]) can be expected to assign the lowest settings for use at home. In other studies of adults, even CPAP at fixed pressure settings for all research subjects, whether healthy or ill, has been safe whether SDB is present or absent.

Families whose children have been randomized to the control group will be contacted by the program manager during the 6-month trial at intervals designed to replicate the frequency of investigator contacts in the CPAP group. Discussion will focus on recuperation after AT, general health, and also any suggestion of serious adverse effects that would warrant discontinuation of study participation and referral for clinical evaluation. These end-points would include recommendation by a child’s pediatrician or otolaryngologist to pursue this option; development of a new, serious cardiopulmonary condition that makes prompt assessment and treatment for any residual SDB imperative; or emergence of serious academic or developmental concerns in the setting of obvious, persistent symptoms of SDB. Each questionable case will be brought by the program manager to the PI and, depending on the nature of the event as outlined in the Data and Safety Management Plan, the DSMB(section 6.5 below) for a decision.

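### The control-arm exit rule ends study participation, and the plan neither keeps those children for the 10-month rating nor handles missing scores in the intent-to-treat test of H2c

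*Combined protocol and SAP*

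**What the plan says.** **Control arm.** Section C3 describes the contacts with control families over the 6 months. Among the topics is "any suggestion of serious adverse effects that would warrant discontinuation of study participation and referral for clinical evaluation". Three kinds of event are listed: a recommendation by the child's pediatrician or otolaryngologist, a new serious cardiopulmonary condition, and "emergence of serious academic or developmental concerns in the setting of obvious, persistent symptoms of SDB". Section 6.2.b repeats the rule ("also any suggestion of serious adverse effects that would warrant discontinuation of study participation and referral for clinical evaluation"). Questionable cases go to the principal investigator. Section 6.1.a adds that a situation in which absence of CPAP poses an urgent threat "will be detected early so that the subject can be removed from the study". The same paragraph expects that "few will leave the protocol to seek clinical care".

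**CPAP arm.** The parallel text in C3 concerns treatment: "Discontinuation of PAP treatment may occur after case consultation with other members of the study team". It does not mention leaving the study. C9 counts about 27 non-adherent children among the 80 CPAP subjects who complete the protocol.

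**Follow-up and analysis.** Aim 2 in section 2.2 says that all subjects are re-assessed. C7(a) makes change in the Behavioral Index under H2c the primary outcome. C8 labels H2c intent-to-treat and regresses the outcome on assigned group, with BMI z-score, age, gender, race and socioeconomic status as covariates. It names no analysis set for children without an SV4 score, no missing-data method and no sensitivity analysis. Drop-outs appear in C8 only in an exploratory comparison of adherent CPAP children with controls. C9 allows for 10% attrition by enrolling 132.

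**The concern.** H2c is the trial's one primary comparison, and its intent-to-treat label means that every randomized child counts as assigned. A rule that ends participation for some controls, partly on grounds close to the outcome, works against that unless the children are still rated. C8 gives no alternative for a missing SV4 score, so the regression would by default use only children who have one.

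The academic or developmental trigger would tend to select controls who are doing badly. Without them the control mean looks better and the CPAP benefit looks smaller. The other triggers have no stated link to the Behavioral Index. The 10% enrollment allowance replaces lost numbers but does not correct for who is lost.

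**Working it through.** **1. The plan's own figure.** Inputs from C9: 80 CPAP v 40 controls, effect size 0.55, power 80%. Alpha is stated there only for H1a, so two-sided 0.05 is assumed for H2c. A two-sample t test gives 80.4%, so the stated power reproduces.

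**2. The texts side by side.**

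| Place | What ends | Is SV4 still collected? |
|---|---|---|
| C3 and 6.2.b, control families | Study participation | Not stated |
| 6.1.a, control with an urgent threat | Place in the study | Not stated |
| C3, CPAP child not progressing | PAP treatment | Implied: C9 counts non-adherent children among completers |
| 2.2, Aim 2 | Nothing | All subjects re-assessed |

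The control rows cannot both end participation and satisfy the Aim 2 statement unless outcome rating continues, and no text says that it does.

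**3. Size of the shift.** The documents give no exit rate by arm, so these inputs are assumptions:
- All 132 are randomized 2:1, so 132 × 2/3 = 88 CPAP and 44 controls.
- 1 or 2 controls leave under the rule, to represent the word few in 6.1.a.
- Their mean change is 1 SD worse than that of the remaining controls (range 0 to 1.5 SD).

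If a share q of controls is missing and is g SD worse than the rest, the full control mean equals the remaining mean minus q × g. An analysis of children with scores therefore shrinks the difference by q × g.

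- 1 of 44, g = 1: 1/44 = 0.023 SD; 0.023/0.55 = 4% of the target difference.
- 2 of 44, g = 1: 2/44 = 0.045 SD; 0.045/0.55 = 8%.
- Extremes: g = 0 gives no shift; 2 of 44 with g = 1.5 gives 0.068 SD, or 12%.

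**4. Power after the shift** (true effect 0.55, g = 1, two-sided t test).

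| Control exits | Apparent effect | Only these children lost | Unrelated losses bring the sample to 80 v 40 |
|---|---|---|---|
| 0 | 0.550 | 84.1% (88 v 44) | 80.4% |
| 1 | 0.527 | 80.3% (88 v 43) | 77% |
| 2 | 0.505 | 76.1% (88 v 42) | 73% |

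The last column assumes that the planned attrition also occurs and is unrelated to outcome. At 2 exits and g = 1.5, power in that column is 69%.

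**The case against.** The best defence is that the gap is narrow. Aim 2 says without exception that all subjects are re-assessed. C8 contrasts its exploratory adherent-v-control comparison with the primary analysis in terms of cross-overs and drop-outs, which suggests that the authors meant such children to count as assigned. Controls may seek outside care without leaving (6.1.c). Few exits are expected, and the team's two earlier studies lost only 5% (C9). C3 also refers these cases to the Data and Safety Management Plan, which was not supplied.

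Most of this stands, and it limits the size of the problem. It does not close it. A general statement about all subjects does not settle what happens to a child whose participation has ended, and intending to count children as assigned supplies no score for those who have none.

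A reader might also infer that outcome-related drop-out in the CPAP arm would offset or reverse the shift and raise the chance of a false CPAP benefit. The text does not support building that in. The remark on "whether the child's current level of anxiety or opposition is elevated" governs only whether to hold a desensitization step, and C9 keeps non-adherent children among the completers. The trial cited in A4, in which "one third of 29 participants aged 2 – 16 years dropped out by 6 months", compared CPAP with bilevel pressure in a wider age range, and it has to be read beside the team's own 5%. CPAP families may withdraw like any others, so loss in that arm is possible, but nothing in the plan sizes it or ties it to outcome.

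**Conclusion.** The point holds as an inconsistency and an omission. The written exit rules differ by arm, the control rule is partly linked to the primary outcome, the document supplied does not keep discontinued controls for SV4, and C8 has no method for missing scores.

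Taken alone, the rule would tend to understate a CPAP benefit. The likely size is 0.02 to 0.05 SD, with power of about 80% to 76%, or 77% to 73% at 80 v 40, against 80% stated. These figures rest on assumed exit counts and an assumed 1 SD gap.

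A reader might infer a serious loss of power. If a tenth of 40 controls left with a 1 SD gap and 80 CPAP scores were kept, 0.55 would fall to 0.45 and power to about 60% (80 v 36). The documents give no ground for that rate and point the other way. Nor is the sample-size calculation wrong. The net direction of bias from all losses in both arms cannot be known from the plan. The change is still worth making, because a rating not collected at SV4 cannot be recovered later.

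**What to change.** 1. Leave the clinical referral criteria unchanged.
2. Reconcile Aim 2 with C3, 6.1.a and 6.2.b: leaving the assigned condition does not by itself end outcome follow-up. If the Data and Safety Management Plan or the manual of procedures already says so, cite it in C3 and C8.
3. Invite discontinued children in either arm to complete at least the SV4 parent rating scales, subject to the family's right to withdraw. C5 already allows electronic forms.
4. In C8, state that H2c is analysed in all randomized children as assigned, and report missing SV4 scores by arm and reason.
5. Prespecify a missing-data method that uses the SV2 Behavioral Index, for example multiple imputation, and a simple sensitivity analysis that varies the assumption about missing scores separately by arm. The exact method and size of shift are for the team to choose.

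The cost is a wording change plus slightly more follow-up and analysis work, since SV4 is already planned for every child. The estimate also takes a treatment-policy meaning, because some discontinued controls will have had outside treatment by the time they are rated.

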Approximately ten months after AT (six months after randomization), sleep studies (on steady PAP for the CPAP subjects, without PAP for controls) and neurobehavioral assessments will all be repeated. The sleep study is required to precede a valid Multiple Sleep Latency Test; will allow confirmation in CPAP subjects that any SDB is well controlled; and will allow reassessment for residual SDB in the control group. The 6-month interval is selected to ensure adequate time for PAP habituation, neurobehavioral response to consistent use of PAP, and acceptably low risk of test-retest learning effects on cognitive measures. The outcome measures have been used by the investigators in two NIH-funded R01s (HD038461 and HL080941) over the past 10 years and all derive from well-validated, widely accepted instruments. The explanatory polysomnographic measures are all consistent with American Academy of Sleep Medicine 2007 standards. Esophageal pressure monitoring, with which this laboratory has extensive clinical, research, and published experience, will be used to provide a gold-standard assessment of respiratory effort. In addition, at least 3 highly innovative, most promising, and particularly sensitive computerized measures, all pioneered previously in children by the investigators, will be available to complement standard analyses. These include respiratory cycle-related EEG changes (RCREC) thought to reflect subtle but numerous and consequential inspiratory microarousals; an analysis of sleep dynamics, which focus on continuity of sleep and specific sleep stage bouts rather than traditional totals of time spent in each stage; and quantitative analysis of esophageal pressure swings during each respiratory cycle through the night. Based on the investigators' preliminary data (see below and section C9.5), these automated measures may well improve the ability of pediatric polysomnography to distinguish children with and without clinically significant SDB and potential to benefit from CPAP.

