An unmasked, board-certified sleep specialist will interpret each sleep study, not to provide study variables but rather to inform families and their physicians. Study results generally will not be communicated until after the participant has finished the entire protocol, when sleep and psychological test results are fully scored. However, an investigator will promptly communicate any finding that could have medically urgent significance for the patient, such as an unsuspected arrhythmia, paroxysmal EEG spikes, or severe residual SDB.

Nocturnal polysomnograms and Multiple Sleep Latency Tests will be scored by a single chief technologist ([name], RPSGT, REEGT) masked to subject identity. This technologist has meticulously scored about 1,000 pediatric sleep research studies in the past 10 years. Borderline polysomnographic features will be arbitrated between the technician and the PI. Scoring will be performed in batches: pre- and post-PAP studies of 5 subjects will be randomly ordered and presented for scoring. This procedure, used for two past R01s, assures that any subtle changes in scoring tendencies over time do not confound pre- vs. post-PAP comparisons. Scoring for sleep stages, respiratory events, periodic leg movements, and arousals will follow standard criteria for children. Double-scoring of arousals and respiratory events, in 20% of the records, will be performed to generate a Kappa statistic for intra-rater reliability. Inter-rater reliability will also be determined by having another experienced polysomnographic technologist score these same records.

For Multiple Sleep Latency Tests, the sleep latency of each nap will be scored as the time between lights out and the first epoch of stage 1 sleep. The mean sleep latency across naps is the most well-validated and commonly used objective measure of daytime sleepiness in both adults and children. Childhood sleepiness as a continuous variable for research purposes can be detected in SDB patients as young as 3 years old by questionnaires and by Multiple Sleep Latency Tests.

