##### **(b) Secondary Outcome Measures:**

1. Neurocognitive change after AT (hypothesis 2c CPAP vs controls intent to treat)

Change in **NIH Toolbox Total Composite Score Age Adjusted** following 6 months of CPAP vs. no CPAP use by children after AT

2. Change in subjective sleepiness after AT (hypothesis 2c CPAP vs controls intent to treat)

Change in **Epworth Sleepiness Scale score** following 6 months of CPAP vs. no CPAP use by children after AT

3. Change in objective sleepiness after AT (hypothesis 2c CPAP vs controls intent to treat)

Change in **MSLT** following 6 months of CPAP vs. no CPAP use by children after AT

4. Change in quality of life (hypothesis 2c CPAP vs controls intent to treat)

Change in **PedsQL** following 6 months of CPAP vs. no CPAP use by children after AT

5. For CPAP subjects, neurobehavioral outcomes will improve more from baseline to follow up among those who have adhered to CPAP than those who are non-adherent (hypothesis 2b)

Change in **behavioral index** from SV2 to SV4 in adherent vs non-adherent CPAP users

6. For CPAP subjects, neurobehavioral outcomes will improve more from baseline to follow up among those who have adhered to CPAP than those who are non-adherent (hypothesis 2b)

Change in **NIH Toolbox Total Composite Score Age Adjusted** from SV2 to SV4 in adherent vs non-adhere

7. For CPAP subjects, neurobehavioral outcomes will improve more from baseline to follow up among those who have adhered to CPAP than those who are non-adherent (hypothesis 2b)

Change in **ESS** from SV2 to SV4 in adherent vs non-adherent CPAP users

8. For CPAP subjects, neurobehavioral outcomes will improve more from baseline to follow up among those who have adhered to CPAP than those who are non-adherent (hypothesis 2b)

Change in **MSLT** from SV2 to SV4 in adherent vs non-adherent CPAP users

9. For CPAP subjects, neurobehavioral outcomes will improve more from baseline to follow up among those who have adhered to CPAP than those who are non-adherent (hypothesis 2b)

Change in **PedsQL** from SV2 to SV4 in adherent vs non-adherent CPAP users

10. Among adherent CPAP users residual SRBD score at SV2 will predict greater improvement at SV4 for behavior (hypothesis 2a)

Change in **behavioral index** from SV2 to SV4 in CPAP adherent subjects will be associated with SRBD score at SV2

11. Among adherent CPAP users residual SRBD score at SV2 will predict greater improvement at SV4 for cognition (hypothesis 2a)

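### C4 masks the single sleep scorer to identity only and does not separate MSLT records from on-PAP night studies, so knowledge of arm could reach the scoring of the objective sleepiness outcome

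*Combined protocol and SAP*

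**What the plan says.** C1 describes the trial as randomised but open. In C4, a single chief technologist scores both nocturnal polysomnograms and MSLTs and is "masked to subject identity". Scoring is done in batches: "pre- and post-PAP studies of 5 subjects will be randomly ordered and presented for scoring". The reason given is that this "assures that any subtle changes in scoring tendencies over time do not confound pre- vs. post-PAP comparisons". Section 6.2.b repeats the drift rationale and adds that the batch is de-identified.

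For the 10-month visit, C3 says that "sleep studies (on steady PAP for the CPAP subjects, without PAP for controls) and neurobehavioral assessments will all be repeated". The MSLT follows the next day. Nap latency runs from lights out until stage 1 is first scored, so it is a staging judgement. Re-scoring of 20% of records for reliability covers arousals and respiratory events; nap latency is not named.

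C4 also says: "Borderline polysomnographic features will be arbitrated between the technician and the PI". C7(b), secondary outcome 3, is "Change in objective sleepiness after AT (hypothesis 2c CPAP vs controls intent to treat"), measured by the MSLT.

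**The concern.** The sleepiness outcomes under H2c are the Epworth score and the MSLT. The Epworth score is a questionnaire in an open trial, so expectation can colour it. The MSLT adds an objective check, but only if whoever marks sleep onset does not know the arm.

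Masking to identity does not ensure that. A night recorded on PAP belongs to a CPAP-arm child at SV4, whatever code it carries and wherever it falls in the batch. If the scorer can tell which MSLT followed that night, that MSLT is unmasked too. A scorer who expects CPAP to reduce sleepiness could then mark sleep onset slightly later in those naps, and the shift would go straight into the CPAP-versus-control contrast. C4 already recognises the principle: the unmasked specialist who reads each study for families does not supply study variables.

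**Working it through.** This is mainly a check of text. The plan gives no SD, effect size or power for the MSLT, so there is no stated figure to reproduce.

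**1. What is masked.** C4: identity. Arm: not stated. Visit: not stated. De-identification (6.2.b) removes names, not PAP signals.

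**2. What the night record reveals.** C3: SV4 nights are on PAP in the CPAP arm and off PAP in controls. An on-PAP night in the scoring batch therefore identifies arm and visit together.

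**3. How many nights.** Inputs from C9: 80 CPAP and 40 control completers, with 53 of the 80 expected to adhere.
- Upper limit, all CPAP children on PAP at SV4: 80/120 = 67% of SV4 nights, or 80/240 = 33% of SV2 and SV4 nights together.
- If only the 53 adherent children are studied on PAP (an assumption; the plan does not say how children who stopped PAP are studied): 53/120 = 44%, or 53/240 = 22%.

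These count nights that reveal arm. They do not count MSLTs known to be unmasked.

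**4. Whether the information can pass to the MSLT.** It could if the night and its MSLT are scored as a linked pair, if PAP signals appear in the nap recording, or if MSLT epochs go to an arbitrator who knows arm. The documents neither state nor exclude any of the three. Section 6.1.a encourages PAP whenever the child sleeps by day, but the plan does not say whether it is worn during test naps.

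**5. What batching does.** Let b be an additive scoring shift common to a batch that holds both visits of a child. The change score is (SV4 + b) − (SV2 + b) = SV4 − SV2, so b cancels. Batching does the job it was designed for. It does nothing about a shift applied only to MSLTs recognised as CPAP-arm SV4.

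**6. What such a shift would do (illustration only).** Assume no true effect and a systematic shift of d SD in MSLT change in the CPAP arm. With a two-sided 5% t test, 80 versus 40 (118 df), the noncentrality is d/√(1/80 + 1/40) = d/0.194. The rejection rates are:

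| Assumed d | Rejection rate |
|---|---|
| 0.05 | 5.8% |
| 0.1 | 8.1% |
| 0.2 | 17.6% |
| 0.3 | 33.6% |

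Nothing in the documents supports any particular d. The table shows only that a small systematic shift would matter at this sample size.

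**The case against.** The strongest reply is that neither apparent leak is documented for the MSLT itself. The PAP signal belongs to the night study. The MSLT is a separate daytime recording with its own scoring rule, and arbitration is worded for polysomnographic features. If coded MSLT files are shuffled apart from their nights, the scorer may be masked in practice, and coding rules may sit in a manual that is not part of these documents. This stands as a limit on the claim: the plan leaves the route open but does not show that it is used. It does not close the gap, because C4 states the masking and stops at identity.

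Three stronger readings are tempting and are not supported.
- A reader might infer that the PI, who rules on control-arm cases ("Each questionable case will be brought by the program manager to the PI (section 6.5) for a decision"), settles MSLT scores knowing the arm. The text does not send MSLT epochs to the PI, and knowing a child's arm does not by itself identify a coded record.
- A reader might infer that batches exclude controls, who have no post-PAP study, so that drift becomes an arm difference. The phrase is more naturally shorthand for the two visits, and additive drift cancels as shown. With independent 2:1 assignment (assumed), a five-child batch would mix arms with probability 1 − (2/3)⁵ − (1/3)⁵ = 210/243 = 86%.
- A reader might take every CPAP-arm SV4 night as on PAP. C3 allows PAP to be discontinued and C9 expects about 27 of 80 to be non-adherent, so 67% is a ceiling.

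**Conclusion.** The point holds as a gap in stated masking. The plan does not mask MSLT scoring to arm or visit, and does not separate MSLT records from night studies that reveal both. Between 44% and 67% of SV4 nights would reveal arm, depending on how many CPAP children are studied on PAP. Whether this knowledge reaches MSLT scoring depends on laboratory practice that the documents do not describe, so the size and even the presence of bias are unknown.

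The reach is limited to secondary outcomes. The primary outcome, the Behavioral Index, is built from parent ratings and is not touched. The change is still worth making, because masked scoring is what gives the MSLT its value beside a questionnaire in an open trial, and the remedy is cheap.

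**What to change.** In C4:
1. Give MSLT recordings their own codes, unlinked to the night study, and score them in separate, randomly ordered batches masked to arm and visit. Keep each child's SV2 and SV4 MSLTs in the same batch, so that drift control is preserved, and state that this applies to both arms.
2. If borderline MSLT epochs are arbitrated at all, send them only as coded extracts without arm or visit.
3. State that scoring of on-PAP SV4 night studies cannot be masked to arm.

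Separate coding works only if the nap recording itself carries no PAP signal, so C4 should say whether it can. The cost is a second coding list and slightly more file handling. The same technologist and the same recordings are used, with no added burden on families.
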